Objective	To examine rates of opioid prescribing, Opioid Use Disorder (OUD) prevalence, and OUD treatment among Oregon Medicaid enrollees after the ACA Medicaid expansion; and to understand how insurance history and dose type are related to OUD diagnosis rates, as well as whether patients with OUD in the expansion population (of new enrollees and those ‘returning’ after coverage gaps) had different MAT participation rates than those previously continuously enrolled.
Study Population	Adults aged 19+64; continuously insured by Oregon Medicaid 1/2014-12/31/2015. N=225,295.
Exclusion Criteria	Patients with coverage gaps during study period; dual eligibles; hospice care; cancer diagnosis other than non-melanoma skin cancer.
Independent Variables	
 1. Insurance group 2. Episode type
Dependent Variables	
 1. Opioid filled prescription 2. Documented diagnosis of OUD 3. Chronic opioid use 4. Receipt of medication assisted treatment
Covariates	Age, sex, race, urban/rural, co-morbidities, zip code, federal poverty level, employment, and number of episodes
Analysis Plan	
 1. Inverse propensity weighting 2. Absolute standardized mean difference 3. Prevalences 4. Logistic regression 5. Cox proportional hazard 6. Multinomial logistic regression
Data Set Name	OUTPAT, OUTPATIENT_2015Q4, RX , RX_Q42015, SAMPLE_FLAGGED_FOR_EXPORT

	hospice_providers, mat_codes, opioid_ndcs_2016
Code Location	Box at OHSU

Following uninsured patients through Medicaid Expansion: healthcare utilization and diagnosed conditions

Full Citation	[name], N., S. Valenzuela, M. Marino, H. Angier, B. Hatch, M. Hoopes and J. E. DeVoe. Following uninsured patients through Medicaid Expansion: healthcare utilization and diagnosed conditions. Submitted Ann Fam Med 11/18.
Objective	Assess healthcare utilization and diagnosed health conditions among a cohort of community health center patients who were uninsured pre-ACA and follow them 24 months post-Affordable Care Act (ACA).
Study Population	All non-pregnant patients without insurance pre-ACA, aged 19-64 during the study period, with ≥ 1 ambulatory visit pre-ACA from 300 primary care CHCs 'live' on their EHR system as of 1/1/2012 in 11 states. N=138,246.
Exclusion Criteria	Pregnant women, insurance coverage prior to ACA.
Independent Variables	1. Insurance group
Dependent Variables	1. Healthcare utilization 2. Health conditions
Covariates	Age, sex, language, race/ethnicity, federal poverty level, and clinic location
Analysis Plan	1. Adjusted predicted probability 2. Mixed effects ordinal logistic regression 3. Random effects to account for clustering visits
Data Set Name	PAT_CONSORT_08312016 encounters_AV1215_pipe FAC_URBRUR STATES PPDA_RUCA_CHARLSON PPDA_PREEXISTING_CONDITIONS Code is under: PPDA Projects -> Who_Remains_Uninsured -> draft4.Rmd
Code Location	Box at OHSU

Utilization of Community Health Centers in Medicaid Expansion and Non-expansion States, 2013-2014.

Full Citation	Hoopes, M. J., H. Angier, R. Gold, S. R. Bailey, N. [name], M. Marino and J. E. DeVoe (2016). Utilization of Community Health Centers in Medicaid Expansion and Non-expansion States, 2013-2014. J Ambul Care Manage 39(4): 290-298.
Objective	Assess CHC utilization a full year before and after the implementation of Affordable Care Act (ACA) Medicaid expansions (24 months) and describes changes in visit type before and after implementation.
Study Population	Adults 19-64 years, billed visits in pre expansion (1/1/13-12/31/13) and post expansion (1/1/14-12/31/14) OCHIN member clinics. N=401,988 patients.
Exclusion Criteria	Pregnant women
Independent Variables	Expansion status
Dependent Variables	1. Insurance status 2. Visit type
Covariates	Sex, age, race/ethnicity, urban/rural, federal poverty level, minimum wage, unemployment, insurance exchange type.
Analysis Plan	1. GEE 2. Poisson models
Data Set Name	OCHIN: e:\sasroot\CATCHUP\ACA 12 month
Code Location	OCHIN SAS server

Effect of Gaining Insurance Coverage on Smoking Cessation in Community Health Centers: A Cohort Study.

Full Citation	Bailey, S. R., M. J. Hoopes, M. Marino, J. [name], J. P. O'Malley, B. Hatch, H. Angier, S. P. Fortmann and J. E. DeVoe (2016). Effect of Gaining Insurance Coverage on Smoking Cessation in Community Health Centers: A Cohort Study. J Gen Intern Med 31(10): 1198-1205.
Objective	To determine if uninsured community health center (CHC) patients who gained Medicaid coverage experienced greater primary care utilization, receive more cessation medication orders, and achieve higher quit rates, compared to continuously uninsured smokers.
Study Population	CHC patients aged 19–64 years who gained Oregon Medicaid coverage between 2008 and 2011 after being uninsured for ≥ 6 months and who maintained this insurance for ≥ 6 months. Cohort of ‘current every day smoker’ or ‘current some day smoker.’

Exclusion Criteria	Non-smoking, pregnant, non-living, private insurance, Medicare insurance.
Independent Variables	Insurance Status
Dependent Variables	1. 'Quit' smoking status (yes/no) 2. Smoking cessation medication ordered (yes/no)
Covariates	Usual source of care after in follow up period.
Analysis Plan	1. Propensity score matching 2. Between group differences 3. GEE for clustering
Data Set Name	Smoking_model_set_PSmatches.sas7bdat
Code Location	OCHIN archive server

Observational Study of Racial/Ethnic Disparities in Health Insurance and Differences in Visit Type for a Population of Patients with Diabetes after Medicaid Expansion.

Full Citation	Angier, H., D. Ezekiel-Herrera, M. Marino, M. Hoopes, E. A. Jacobs, J. E. DeVoe and N. [name] (In press). Observational Study of Racial/Ethnic Disparities in Health Insurance and Differences in Visit Type for a Population of Patients with Diabetes after Medicaid Expansion. J Health Care Poor Underserved.
Objective	To understand the impact of the Affordable Care Act (ACA) Medicaid expansion on racial/ethnic health insurance disparities and differences in visit type for a population of patients with diabetes, by assessing changes pre- versus post-ACA in expansion compared with non-expansion states.
Study Population	Adults aged 19-64, diabetes diagnosis any time during study period, CHCs in ADVANCE network with EHRs live as of January 2013.
Exclusion Criteria	Pregnant women
Independent Variables	Expansion status
Dependent Variables	1. Health insurance status 2. Healthcare visit types a. Total b. Type
Covariates	Sex, age, FPL, Charlson comorbidity index score, state-level factors
Analysis Plan	1. Incidence rates 2. GEE Poisson models 3. Difference in Difference

Data Set Name	Analytic Data: PPDA Projects → PACE → Diabetes Disparities → Analytic Data Code: PPDA Projects → PACE → Diabetes Disparities → Code
Code Location	Box at OHSU

Assessing the prevalence of pre-existing conditions among community health center patients.

Full Citation	[name], N., H. Angier, M. J. Hoopes, M. Marino, J. [name], T. Schmidt and J. E. DeVoe. Assessing the prevalence of pre-existing conditions among community health center patients. Medical Care. Submitted 9/18
Objective	To assess the prevalence of pre-existing conditions pre- versus post-Affordable Care Act (ACA) for community health center (CHC) patients who gained insurance

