Statistical Analysis Plan (SAP)

The PACE Study

Post Affordable Care Act: Evaluation of Community Health Centers

[figure not shown]
AHRQ R01HS024270
NCT 02657499

January 1, 2019

**A partnership between:
Oregon Health & Science University
OCHIN, Inc.**

B.4.4 Statistical Analysis.

We will use validated OCHIN data and Medicaid claims data to assess the impact of Medicaid expansion on healthcare access, receipt of healthcare services, and Medicaid expenditures. We will summarize baseline measures using descriptive statistics and data visualization methods (e.g., histograms, scatter plots) across clinic and state groups. Our primary criteria for studying Medicaid expansion will be estimating differences in outcomes described in Box 7 (above) between individuals and clinics in (a) expansion versus non-expansion states over the 12-months pre- and at least 24-months post-Medicaid expansion time periods (Aim 1), (b) in expansion states only (Aim 2), and (c) in Oregon (Aim 3). As seen in Box 8, the ACA-Medicaid expansion took effect January 1, 2014. Eight states in the OCHIN EHR data adopted Medicaid expansion at the start of 2014. Their pre-period is 12-months prior to 2014 (i.e., 2013) and their post-period extends from the time of expansion to the end of the project. (For most expansion states, the post-period will be 2014 through 2017; however, we are aware that some non-expansion states may expand during the study period, so we will take this into account in our analyses). Our primary methodological approach will utilize difference-in-differences (DID) methodology. The DID approach has been frequently used by health services researchers to account for potential secular effects and changing policies that would affect both expansion and non-expansion states over time, while adjusting for potential confounders.¹⁶⁷⁻¹⁷²

The general analysis for **Aim 1** is represented by the following equation:

$$Y_{ijkt} = f(\alpha + \beta M_k + \gamma \tau_t + \theta M_k \tau_t + \delta Z_{ijkt})$$

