where Y_{ijkt} represents individual i 's performance on an outcome measure of interest (i.e., insurance coverage,) nested within the j th clinic in state k at time t ; M_k represents a dummy variable taking a value of 1 in expansion-state and zero otherwise; and τ_t is a dummy variable taking a value of 1 if the observation took place after Medicaid expansion and 0 otherwise, Z_{ijkt} is a matrix of potential individual, clinic, or state confounders and f represents a general function that captures our intent to model a variety of outcome types through generalized linear mixed models (GLMMs).¹⁷³ The coefficient α is an overall intercept representing average baseline performance for all individuals; β represents the incremental baseline performance differential between clinics in expansion and non-expansion states and γ represents the change in performance pre- and post-expansion for all clinics. The coefficient of interest θ captures the relative performance improvement in outcomes for the patients in expansion versus non-expansion states over time. In this model, non-expansion states will serve as the reference. This equation is very general but can be adapted to include dummy variables for each time period or a continuous variable to capture linear time trends.

To address Aims 2 and 3, we can use a modification of the equation presented above. For **Aim 2**, the indicator M_k will be replaced with two indicator variables to represent the three insurance groups (newly insured, already insured, and uninsured) of interest. For **Aim 3**, the indicator M_k will be substituted by a binary variable denoting newly insured versus already insured. This equation can also be adapted to have the clinic serve as the unit of measurement instead of the individual. There are multiple options for estimating our DID approach. Our preferred method is to implement state random effects in clinic-level analyses and both clinic and state random effects in patient-level analyses to control for correlation of observations nested in clusters (e.g., individuals nested in clinics which are nested in states). Clinics and

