Full Citation	[name], N., Hoopes, M. J., Angier, H., Marino, M., Holderness, H., & DeVoe, J. E. (2017) Medicaid Expansion Produces Long-Term Impact on Insurance Coverage Rates in Community Health Centers. J Prim Care Community Health. 8(4):206-212.
Objective	Assess change in insurance coverage rates pre- and post-ACA in Medicaid expansion and non-expansion states for community health center patients.
Study Population	N=875,571 patients; Inclusion: ages 19-64 with ≥ 1 visit between 2012 and 2015. Setting: 412 primary care CHCs in 9 expansion and 4 non-expansion states.
Exclusion Criteria	Pregnant women
Independent Variables	Whether state had taken Medicaid expansion as of January 1, 2014.
Dependent Variables	Health care delivery: rates of billed encounters (all, primary care, new patient, established patient), receipt of preventive services (preventive medicine visits, immunizations, medications ordered). 1. Insurance type: uninsured, Medicaid-insured, privately-insured.
Covariates	Clinic-level: distributions of sex, age, race/ethnicity, primary language, federal poverty level. State-level: marketplace type, 2013 minimum wage, 2013 uninsured rate, 2013 unemployment rate.
Analysis Plan	Post- versus pre-expansion rate ratios within expansion group; difference-in-difference ratios (comparing post- versus pre-period changes between expansion states vs non-expansion states); and second year post- (2015) versus first year post-ACA (2014) rate ratios within expansion group.
Data Set Name	OCHIN: e:\sasroot\PPDA\P_Huguet_24mo
Code Location	OCHIN SAS server

Oregon Medicaid Expenditures After the 2014 Affordable Care Act Medicaid Expansion: Over-time Differences Among New, Returning, and Continuously Insured Enrollees

Full Citation	Springer, R., Marino, M., O'Malley, J. P., Lindner, S., [name], N., & DeVoe, J. E. (2018). Oregon Medicaid Expenditures After the 2014 Affordable Care Act Medicaid Expansion: Over-time Differences Among New, Returning, and Continuously Insured Enrollees. Med Care, 56(5) , 394-402.
Objective	To assess health care expenditures among Medicaid enrollees in the 24 months after Oregon's 2014 Medicaid expansions and examine whether expenditure patterns were different among the newly, returning, and continuously insured.
Study Population	Oregon adult Medicaid beneficiaries insured continuously from 2014 to 2015 who were either newly, returning, or continuously insured.

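### The coverage paper's only 2015-versus-2014 contrast has no comparator, so it cannot show whether the expansion effect persisted or faded

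*Combined protocol and SAP*

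**What the plan says.** The entry for this paper in the Combined protocol and SAP (Data Analyses, first table) gives the objective as "Assess change in insurance coverage rates pre- and post-ACA in Medicaid expansion and non-expansion states for community health center patients". Its Analysis Plan row lists three contrasts:

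1. "Post- versus pre-expansion rate ratios within expansion group"
2. "difference-in-difference ratios (comparing post- versus pre-period changes between expansion states vs non-expansion states"
3. "second year post- (2015) versus first year post-ACA (2014) rate ratios within expansion group"

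A comparator is available: "Setting: 412 primary care CHCs in 9 expansion and 4 non-expansion states", with patients included if seen between 2012 and 2015. The dated state-level covariates (minimum wage, uninsured rate, unemployment rate) are all 2013 values.

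The SAP, section B.4.4, adopts DID "to account for potential secular effects and changing policies that would affect both expansion and non-expansion states over time". It adds that the Aim 1 equation "can be adapted to include dummy variables for each time period". No year-specific DID appears in this paper's entry.

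**The concern.** The title, "Medicaid Expansion Produces Long-Term Impact on Insurance Coverage Rates in Community Health Centers", invites the question whether the effect held into the second year. Contrast 3 is the only listed contrast that isolates that year, and it is the one without a control group. The SAP's stated reason for using DID applies as much to 2014-to-2015 change as to pre-to-post change. The covariates do not help, because values fixed at 2013 cannot track movement between 2014 and 2015.

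For Aim 3, by contrast, the SAP plans comparisons between successive post-expansion years and relies on the already insured group to remove secular change. The coverage paper has a comparison group but does not use it for its year-on-year contrast. What is at stake is any statement that the effect lasted, grew or faded. The overall post-versus-pre effect is not in question.

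**Working it through.** The documents give no rates, power or sample size for this contrast, so there is no planned figure to reproduce. The check is algebraic, and every effect and trend value below is assumed.

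**Model.** Let M = 1 in expansion states, and let Y14 and Y15 indicate the two post years:

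log rate = a + bM + g14·Y14 + g15·Y15 + t14·M·Y14 + t15·M·Y15

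Here g is the trend common to both groups and t is the expansion effect in each year.

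- Within-expansion 2015/2014 ratio (contrast 3) = exp(g15 − g14) × exp(t15 − t14), that is, secular change × change in effect.
- The same ratio in non-expansion states = exp(g15 − g14).
- Dividing the first by the second leaves exp(t15 − t14), the change in effect alone, provided the two groups share the trend.

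**Step 1: a trend with no change in effect.** Set the effect to 1.5 in both years.

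| Common 2015/2014 change | Contrast 3 | 2015-versus-2014 DID ratio |
|---|---|---|
| 0.90 | 0.90 | 1.00 |
| 0.95 | 0.95 | 1.00 |
| 1.00 | 1.00 | 1.00 |
| 1.05 | 1.05 | 1.00 |
| 1.10 | 1.10 | 1.00 |

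Contrast 3 simply returns the trend.

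**Step 2: a trend that hides fading.** Let the effect fall from 1.50 to 1.50/1.10 = 1.364, with a common change of 1.10. Contrast 3 = 1.10 × 1.364/1.50 = 1.00, so nothing appears to change. The DID ratio is 1.364/1.50 = 0.91.

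**Step 3: one observed ratio, three readings.** Suppose contrast 3 for uninsured visits is 0.90. The year-2-versus-year-1 DID ratio then depends on the unreported ratio in non-expansion states:

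- 0.95 gives 0.90/0.95 = 0.95
- 0.90 gives 0.90/0.90 = 1.00
- 0.85 gives 0.90/0.85 = 1.06

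For uninsured visits these mean, in order, a further fall relative to the comparator, no change, and fading.

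**Step 4: can contrast 2 fill the gap?** Assume it pools 2014 and 2015 with equal weight, and assume no secular trend. The pooled DID ratio is the mean of the two yearly effects:

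- stable, 1.5 and 1.5: (1.5 + 1.5)/2 = 1.50
- fading, 1.8 and 1.2: (1.8 + 1.2)/2 = 1.50
- growing, 1.2 and 1.8: (1.2 + 1.8)/2 = 1.50

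A pooled DID cannot tell these apart. It does remove a common trend from the overall effect: in every row of step 1 it equals 1.50.

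**The case against.** A reader might infer that the paper tests durability with contrast 3 and would read any secular trend as a lasting effect of expansion. The documents do not support that:

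- The entry never calls contrast 3 a test of durability and gives no rule for interpreting it.
- The stated objective is pre-to-post change in both groups of states, and the DID ratio in the same row answers it with a comparator.
- The long-term claim appears only in the title. It may mean no more than 24 months of follow-up: this paper's data set name refers to 24 months, while that of the separate 2013-2014 utilization paper refers to 12. On that reading the title rests on the controlled DID and contrast 3 is a supplement.
- Pooling of 2014 and 2015 in the DID is an inference. The entry does not define the post-period; a two-year post-period appears only in the general Data Sources text.
- The entry is a short summary of a paper cited as published in 2017, and its full methods are not in these documents.

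All of this stands, and it limits the point. The paper's overall effect estimate is not uncontrolled, and the bias in contrast 3 has no fixed direction.

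The remedy also has limits. It relies on 4 unnamed comparator states. Table 2 lists Indiana (expanded 2/1/2015) and Alaska (expanded 9/1/2015) under non-expansion and says only that they were left out of some analyses. Either one would contaminate the comparator in the very year to be isolated.

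None of this supplies a controlled comparison of year 2 with year 1.

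**Conclusion.** The point holds in a limited form. The only listed contrast that separates 2015 from 2014 is confined to expansion states, so it cannot distinguish a change in the expansion effect from a secular trend. Such a trend could mimic or hide either persistence or fading. The listed DID ratio protects the overall post-versus-pre effect against common trends, but if it pools the two post years it says nothing about persistence.

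The size is illustrative only: contrast 3 is off by exactly the common 2014-to-2015 change, so a 10% trend gives a 10% error in the ratio. This rests on a multiplicative model, a trend shared by the two groups and, for the statement about the DID, pooling over 2014-2015. No bias in the actual results has been shown. The change should be made before any claim about lasting impact is based on this analysis.

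**What to change.** In the model that yields the DID ratio, split the post-period indicator into 2014 and 2015 and interact each with expansion status. Report three quantities with intervals:

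- the DID ratio for 2014 versus pre, exp(t14);
- the DID ratio for 2015 versus pre, exp(t15);
- their ratio, exp(t15 − t14), which is 2015 versus 2014, expansion over non-expansion.

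Base any statement about lasting impact on these. Keep the within-expansion 2015/2014 ratio, labelled descriptive. State the pre- and post-periods used in the DID. Name the 4 comparator states and confirm that none expanded during 2015; if Indiana or Alaska is among them, exclude it or censor it from its expansion date.

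The cost is small: one more period term and one more interaction, on data already held and within the adaptation that the SAP allows. Because the paper is already published, this would be a supplementary analysis. The price is a wider interval than for the uncontrolled ratio, and reliance on parallel trends from 2014 to 2015 across only 4 comparator states. The uncontrolled ratio, read as a change in effect, needs the stronger assumption of no trend at all.
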